6.3 FOLLOW-UP PHASE

After study Treatment Phase is completed, all subjects will enter the Follow-up Phase. The Follow-up Phase will comprise of the following:

- Safety Follow-up Visit
- Post-treatment Phase
- Post-disease Progression Phase

6.3.1 Safety Follow-up Visit

The Safety Follow-up Visit will be conducted prior to the start of a new anticancer treatment or 30 (±7) days after the last PCI-32765 dose, whichever occurs first, to monitor for ongoing AEs (refer to Section 7.0) and to document the occurrence of any new AEs. The Schedule of Assessments (Appendix 3) describes the procedures required for the Safety Follow-up Visits.

6.3.2 Post-treatment Phase

The Post-treatment Phase will extend from the discontinuation of treatment up until the subject has progressive disease or other criteria listed in Section 4.3. Subjects will be followed approximately every 3 months (±7 days) for disease progression and initiation of any subsequent anticancer therapy.

6.3.3 Post-disease Progression Phase

After disease progression, follow subject for survival status (including cause of death) by clinic visit or phone contact, as well as collection of subsequent anticancer therapy once every 3 months (± 7 days) until the end of study.

6.4 MISSED EVALUATIONS

Missed evaluations should be rescheduled and performed as close to the original scheduled date as possible. An exception is made when rescheduling becomes, in the investigator's opinion,

medically unnecessary or unsafe because it is too close in time to the next scheduled evaluation. In that case, the missed evaluation should be abandoned.

7.0 ASSESSMENT OF SAFETY

Safety assessments will consist of monitoring and recording Grade 3 or 4 AEs, SAEs, AEs of special interest (Section 7.2.4) and measurements of protocol-specified physical exam; and other tests to ensure patient safety.

7.1 **DEFINITIONS**^{14,15}

7.1.1 Adverse Events

An AE is any untoward medical occurrence in a subject administered a pharmaceutical product and which does not necessarily have a causal relationship with this treatment. An AE can therefore be any unfavorable and unintended sign (including an abnormal laboratory finding, for example), symptom, or disease temporally associated with the use of an investigational study drug, whether or not considered related to the study drug.

For the purposes of this clinical study, AEs include only grade 3 or 4 events which are either new or represent detectable exacerbations of pre-existing conditions or events of special interest (see protocol Section 7.2.4).

The following are exceptions that will be collected as AE's regardless of severity grade:

- AE leading to dose reduction
- AE leading to treatment discontinuation
- SAE
- Other malignancies
- Eye-related adverse events Grade 2 or higher

Disease progression is not an adverse event; rather it may be the cause of an adverse event. Adverse events that occur due to disease progression must be reported as all other treatment-emergent adverse events. "Disease progression" should never be an adverse event term.

Adverse events may include, but are not limited to:

- Subjective or objective symptoms provided by the subject and/or observed by the investigator or study staff including laboratory abnormalities of clinical significance.
- Any AEs experienced by the subject through 30 days after last dose of study drug.
- AEs not previously observed in the subject that emerge during the protocol-specified AE reporting period, including signs or symptoms associated with the underlying disease that were not present before the AE reporting period (refer to Section 7.2.1).

• Complications that occur as a result of protocol-mandated interventions (e.g., invasive procedures such as biopsies).

The following are NOT considered an AE:

- **Pre-existing condition:** A pre-existing condition (documented on the medical history case report form [CRF]) is not considered an AE unless the severity, frequency, or character of the event worsens during the study period.
- Preplanned or elective hospitalization: A hospitalization planned before signing the informed consent form is not considered an SAE, but rather a therapeutic intervention. However, if during the pre-planned hospitalization an event occurs, which prolongs the hospitalization or meets any other SAE criteria, the event will be considered an SAE. Surgeries or interventions that were under consideration but not performed before enrollment in the study will not be considered serious if they are performed after enrollment in the study for a condition that has not changed from its baseline level. Elective hospitalizations for social reasons, solely for the administration of chemotherapy, or due to long travel distances are also not SAEs.
- **Diagnostic Testing and Procedures:** Testing and procedures should not to be reported as AEs or SAEs, but rather the cause for the test or procedure should be reported.
- Asymptomatic Treatment-Related Lymphocytosis: This event should also not be considered an AE. Subjects with treatment-related lymphocytosis should remain on study treatment and continue with all study-related procedures.

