5.4.2 Dose Reduction and Discontinuation

At the discretion of the investigator, based upon the recent FDA approvals of IMBRUVICA® (PCI-32765) for the treatment of MCL and CLL after having received at least one prior therapy and for the treatment of WM, subjects may have their PCI-32765 dose reduced to the approved dosage in the absence of toxicity. Any subsequent dose modifications below the approved label dose should follow the dose modification guidelines per protocol for toxicity.

The actions in Table 1 should be taken for the following toxicities:

• Grade 4 ANC ($< 500/\mu$ L) for > 7 days (neutrophil growth factors are permitted per ASCO guidelines ¹⁶ and use must be recorded in CRF).

- Grade 3 thrombocytopenia ($< 50,000/\mu L$) in the presence of clinically significant bleeding events.
- Grade 4 thrombocytopenia (< 25,000/μL).
- Grade 3 or 4 nausea, vomiting, or diarrhea, if persistent despite optimal antiemetic and/or anti-diarrheal therapy.
- Any other Grade 4 toxicity or any unmanageable Grade 3 toxicity.

For Grade 3 or 4 atrial fibrillation or persistent atrial fibrillation of any grade, consider the risks and benefits of PCI-32765 treatment. If clinically indicated, the use of anticoagulants or antiplatelet agents may be considered for the thromboprophylaxis of atrial fibrillation (Section 5.6.4).

Table 1: Drug Discontinuation Actions for Subjects on PCI-32765

Occurrence	Action
1 st	Hold PCI-32765 until recovery to Grade ≤ 1 or baseline; may restart at original dose level
2 nd Hold PCI-32765 until recovery to Grade ≤ 1 or baseline; restart at one dose level lower (140mg less daily)*	
3 rd	Hold PCI-32765 until recovery to Grade ≤ 1 or baseline; restart at one dose level lower (140mg less daily)*
4 th	Discontinue PCI-32765

^{*} Reference Table 2 for details on dose de-escalation of 420, 560 and 840 mg dose group.

Changes must be recorded in the Dose Administration eCRF and subject's records.

A high number of circulating malignant cells (>400000/mcL) may confer increased risk of leukostasis; these subjects should be closely monitored. Administer supportive care such as hydration and/or leukophoresis as indicated. PCI-32765 may be temporarily held, and medical monitor should be contacted.

Table 2: Intrasubject Dose De-escalation

Assigned Daily Dose	420 mg	560 mg	840 mg
	(3 x 140-mg)	(4 x 140-mg)	(6 x 140-mg)
Dose De-escalation Level 1	280 mg	420 mg	700 mg
	(2 x 140-mg)	(3 x 140-mg)	(5 x 140-mg)

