5.6.4 Concomitant Use of Antiplatelet Agents and Anticoagulants

Warfarin or vitamin K antagonists should not be administered concomitantly with PCI-32765. Supplements such as fish oil and vitamin E preparations should be avoided. Use PCI-32765 with caution in subjects requiring other anticoagulants or medications that inhibit platelet function. Subjects with congenital bleeding diathesis have not been studied. For guidance on PCI-32765 and the use of anticoagulants during procedures/surgeries see Section 5.6.5.

Subjects requiring the initiation of therapeutic anticoagulation therapy (e.g., atrial fibrillation), consider the risks and benefits of continuing PCI-32765 treatment. If therapeutic anticoagulation is clinically indicated, treatment with PCI-32765 should be held and not be restarted until the subject is clinically stable and has no signs of bleeding. No dose reduction is required when study drug is restarted.

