6.1 DESCRIPTION OF PROCEDURES

Informed Consent

Screening

The subject must read, understand and sign the IRB-approved informed consent form (ICF) confirming his or her willingness to participate in this study before initiating any screening activity that is not standard of care. Subjects must also grant permission to use protected health information.

Medical History

Screening

Medical history, concomitant medications, and any ongoing signs or symptoms from the prior PCI-32765 protocol must be recorded in the site's source documentation.

Adverse Events

At all visits (except Post-treatment and Post-PD follow up assessments)

The accepted regulatory definition for an AE is provided in Section 7.1. Adverse events that meet the criteria for SAEs, events of special interest (Section 7.2.4), and AEs of grade 3 or higher in severity will be recorded from the subject's first dose of study drug until 30 days after study drug discontinuation or start of a new anticancer therapy. Important additional requirements for reporting SAEs are explained in Section 7.2.

Concomitant Medication Use

At screening visit and during study when associated with protocol specified AE or SAE. Verify concomitant medication use to ensure subjects' eligibility to remain on study and when associated with a protocol specified AE/SAE. See Section 7.0 for further AE/SAE details.

Confirmation of Eligibility

Screening

Perform all necessary procedures and evaluations to document that the subject meets each eligibility criterion. Screening evaluations must be completed within 14 days before the subject's first dose of PCI-32765 under this protocol.

Physical Examination and Vital Signs

At all visits (except Post treatment and Post PD follow up assessments)

The screening physical examination will include, at a minimum, the general appearance of the subject, height (screening only) and weight, and examination of the skin, eyes, ears, nose, throat, lungs, heart, abdomen, extremities, musculoskeletal system, nervous system, and lymphatic system.

Symptom-directed physical exams will be done during the treatment period and at the Safety Follow-up Visit.

Vital signs will include blood pressure, pulse, respiratory rate, and body temperature. Vital signs and weight will be measured at every visit. Screening vital signs and weight do not need to be repeated if performed on prior PCI-32765 protocol within 14 days before the first administration of study drug on this protocol.

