7.2.4.1 Major Hemorrhage

Major hemorrhage is defined as any of the following:

- Any treatment-emergent hemorrhagic adverse events of Grade 3 or higher. a.
- Any treatment-emergent serious adverse events of bleeding of any grade

- Any treatment-emergent central nervous system hemorrhage/hematoma of any grade
- a. All hemorrhagic events requiring transfusion of red blood cells should be reported as grade 3 or higher AE per CTCAE.

Events meeting the definition of major hemorrhage will be captured as an event of special interest according to Section 7.2.4 above.

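### Section 7.1.1 does not require collection of non-serious Grade 1–2 atrial fibrillation that leads to a dose hold, although the protocol itself acts on such events

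*Protocol*

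**What the plan says.** **What is collected.** Protocol section 7.1.1 defines AEs narrowly for this study: "AEs include only grade 3 or 4 events which are either new or represent detectable exacerbations of pre-existing conditions or events of special interest". It then lists five exceptions that fall outside this grade limit:
- "AE leading to dose reduction"
- "AE leading to treatment discontinuation"
- SAEs
- other malignancies
- "Eye-related adverse events Grade 2 or higher"

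Under section 7.2.4 only one event of special interest is defined: "Events meeting the definition of major hemorrhage will be captured as an event of special interest". Appendix 3 footnote k refers back to the 7.1.1 exceptions. The synopsis, section 6.1 and section 7.0 do not. Section 6.1, for example, lists SAEs and then says that "events of special interest (Section 7.2.4), and AEs of grade 3 or higher in severity will be recorded".

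**What the protocol acts on.** Section 5.4.2 states: "For Grade 3 or 4 atrial fibrillation or persistent atrial fibrillation of any grade, consider the risks and benefits of PCI-32765 treatment". Section 5.6.4, with atrial fibrillation as its example of a reason to start anticoagulation, states: "If therapeutic anticoagulation is clinically indicated, treatment with PCI-32765 should be held". It adds that the dose need not be lowered on restart. Section 5.4.1 also holds drug until the subject is stable on an anticoagulant. Neither anticoagulation hold has an AE grade threshold.

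**What the data are for.** The primary endpoint (3.2) is how often AEs occur, how severe they are and whether they are related to treatment. Section 8.0 summarizes AE incidence descriptively, with no hypothesis test.

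**The concern.** Collecting mainly Grade 3 and above is a legitimate choice for an extension study. The difficulty is that the exceptions follow a visible logic, and that logic stops one step short. They pick up lower-grade events that change treatment by reduction or discontinuation, and risks the sponsor is watching (malignancies, eye events). A hold also changes treatment. Atrial fibrillation is also a listed risk (1.4.3.5), and 5.4.2 singles it out at any grade.

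The completeness of the AE count for that risk is at stake, and the AE count is the primary endpoint. An event that is never entered cannot be recovered at analysis, and a later reader of the tables could not tell that these cases were outside the collection rule.

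**Working it through.** No sample size, power or error rate is stated, so there is no planned figure to reproduce. The check sets the collection rule against the action rules, and then asks whether the size can be bounded.

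**Step 1. Trace one case.** Take a new, non-serious Grade 1 or 2 atrial fibrillation that leads to anticoagulation, a hold, and a restart at the same dose.

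| Route into the AE data | Met? |
|---|---|
| Grade 3 or 4 (7.1.1) | No, by grade |
| Event of special interest (7.2.4) | No; only major hemorrhage is defined |
| Dose reduction | No; 5.6.4 requires none on restart |
| Treatment discontinuation | No; drug is restarted |
| SAE | No; non-serious by construction |
| Other malignancy, or eye event of Grade 2 or higher | No |
| Ongoing AE from the parent study (synopsis, 7.2.1) | No; the event is new |

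No route applies. Section 7.2.2 says that all AEs go on the AE eCRF, but it relies on the restricted definition in 7.1.1 and so does not reopen the door.

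**Step 2. Look for another record.**
- Concomitant medication: after screening, 6.1 and Appendix 3 require recording only when the drug is linked to a protocol-specified AE or an SAE. With no such AE, the anticoagulant need not be recorded.
- ECG: performed at the investigator's discretion (6.1), so there is no scheduled series to search.
- Dosing: 5.4.2 sends dose changes to the Dose Administration eCRF. The hold may appear there, but without a matching AE record.

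**Step 3. How wide is the dose-hold gap?** The toxicity hold in 5.4.1 starts at Grade 3. Every trigger for Table 1 in 5.4.2 is Grade 3 or 4. The AEs behind those holds are already collected by grade. What remains is holds tied to non-serious Grade 1–2 events, most clearly the anticoagulation hold for atrial fibrillation.

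**Step 4. Can the size be bounded?** Section 1.4.1 gives pooled monotherapy rates for N = 1061:
- Grade 3 or 4 atrial fibrillation: 0.026 × 1061 = 27.6, about 28 subjects.
- Atrial fibrillation SAEs: 0.028 × 1061 = 29.7, about 30 subjects.

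The overlap is not given. The share of subjects collected as Grade 3–4 or serious therefore lies between 2.8% (full overlap) and 2.6% + 2.8% = 5.4% (no overlap). The any-grade rate is not given either. Assuming it for illustration only, the share collected is the collected rate divided by the any-grade rate:

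| Assumed any-grade rate | Share collected at 2.8% | Share collected at 5.4% |
|---|---|---|
| 4% | 70% | 100% (capped) |
| 6% | 47% | 90% |
| 8% | 35% | 68% |
| 10% | 28% | 54% |

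Lower-grade cases that lead to reduction or discontinuation would raise these shares. A span from 28% to 100% shows that the document does not fix the size. One thing does follow from the stated rates: 30 − 28 = 2, so at least about two subjects had serious atrial fibrillation that was not Grade 3 or 4. Grade alone does not separate the important cases from the rest.

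**The case against.** The strongest reply is that this is a choice of scope. Restricted collection is stated openly throughout the protocol and fits the aim in 1.5 of lowering the burden on subjects. Nowhere does the protocol promise to capture every atrial fibrillation or every AE that alters dosing, so nothing is contradicted. That stands, and the point is therefore an improvement to the exceptions list rather than an error.

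Some low-grade cases will also be caught. If the review under 5.4.2 ends in reduction or discontinuation, the AE is collected. The definition in 7.1.2 lets the investigator or the sponsor class an important medical event as serious. This narrows the gap but does not close it: it depends on judgment, and the sponsor can judge only what has been reported to it.

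Several stronger readings are tempting, and the documents do not support them:
- **Dose holds in general go uncollected.** They do not; see the Grade 3 triggers in 5.4.1 and Table 1.
- **A third to 60% of cases are missed.** This follows if lower-grade cases are 0.5 to 1.5 times as frequent as Grade 3–4, using r/(1 + r). No such ratio is given, and the formula counts only Grade 3–4 as collected. With 2.8% to 5.4% collected, r = 0.5 adds 1.3% missed, a share of 19% to 32%; r = 1.5 adds 3.9%, a share of 42% to 58%. Even these ignore cases caught through reduction or discontinuation.
- **Holds cannot be attributed to a cause.** The dosing eCRF is not shown and may have a reason field.
- **The tolerability endpoint is damaged.** Section 3.3 measures it by treatment-related SAEs and discontinuations due to AEs, both collected at any grade.
- **Sections 6.1 and 7.0 ignore the exceptions entirely.** Both name SAEs, and 6.1 points to 7.1 for the definition. Their summaries are incomplete, not empty.
- **The protocol calls atrial fibrillation a long-term risk.** Section 1.4.3.5 lists it as a risk and says nothing about late onset.

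**Conclusion.** The point holds in a narrow form. The collection rule leaves out a category of event on which the protocol itself acts: new, non-serious Grade 1–2 atrial fibrillation managed by anticoagulation, a hold and a same-dose restart. The direction is certain, an under-count of atrial fibrillation in the primary endpoint. The size is unknown, and no percentage should be attached to it without an any-grade rate. The conclusion assumes that sites follow 7.1.1 as written and that no eCRF instruction outside the protocol widens it. It is a modest weakness that is cheap to repair.

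**What to change.** Add two items to the exceptions in 7.1.1: *AE leading to dose hold or interruption*, and *atrial fibrillation or flutter of any grade*. Cite that list in the synopsis, 6.1 and 7.0, as Appendix 3 footnote k already does. Once these are protocol-specified AEs, the existing concomitant-medication rule also brings in the associated anticoagulant, with no further change.

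The cost is two lines, three cross-references and a modest number of extra AE and medication records. No visit or test is added. The change concerns data collection only; it proposes no change to any hold, restart or anticoagulation rule.

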7.1.2 Serious Adverse Event

The terms "severe" and "serious" are not synonymous. Severity (or intensity) refers to the grade of an AE (see below). "Serious" is a regulatory definition.

An SAE (experience) or reaction is any untoward medical occurrence that at any dose:

- results in death (i.e., the AE actually causes or leads to death)
- is life-threatening ("life-threatening" is defined as an AE in which the subject was at risk of death at the time of the event. It does not refer to an event which hypothetically might have caused death if it were more severe. If either the investigator or the Sponsor believes that an AE meets the definition of life-threatening, it will be considered life-threatening.)
- requires inpatient hospitalization >24 hours or prolongation of existing hospitalization
- results in persistent or significant disability/incapacity (i.e., the AE results in substantial disruption of the subject's ability to conduct normal life functions)
- is a congenital anomaly/birth defect
- is an important medical event that may not result in death, be immediately life-threatening or require hospitalization, but may be considered an SAE when, based upon appropriate medical judgment, the event may jeopardize the patient, or patient may require intervention to prevent one of the other outcomes listed in this definition. Examples of such events are intensive treatment in an emergency department or at home for allergic bronchospasm, blood dyscrasias, or convulsion that does not result in hospitalization; or development of drug dependency or drug abuse.

Given that the investigator's perspective may be informed by having actually observed the event, and the Sponsor is likely to have broader knowledge of the drug and its effects to inform its evaluation of the significance of the event, if either the Sponsor or the investigator believes that the event is serious, the event will be considered serious.

7.1.3 Severity

Definitions found in the Common Terminology Criteria for Adverse Events (CTCAE) v4.03 will be used for grading the severity (intensity) of AEs. The CTCAE v4.03 displays Grades 1 through 5 with unique clinical descriptions of severity for each referenced AE. Should a subject experience any AE not listed in the CTCAE v4.03, the following grading system should be used to assess severity:

- Grade 1 (Mild AE) experiences which are usually transient, requiring no special treatment, and not interfering with the subject's daily activities.
- Grade 2 (Moderate AE) experiences which introduce some level of inconvenience or concern to the subject, and which may interfere with daily activities, but are usually ameliorated by simple therapeutic measures.
- Grade 3 (Severe AE) experiences which are unacceptable or intolerable, significantly interrupt the subject's usual daily activity, and require systemic drug therapy or other treatment.
- Grade 4 (Life-threatening or disabling AE) experiences which cause the subject to be in imminent danger of death.
- Grade 5 (Death related to AE) experiences which result in subject death.

7.1.4 Causality

The investigator is to assess the causal relation (i.e., whether there is a reasonable possibility that the study drug caused the event) using the following definitions:

Unrelated: Another cause of the AE is more plausible; a temporal sequence cannot

be established with the onset of the AE and administration of the investigational product; or, a causal relationship is considered

biologically implausible.

Possibly Related: There is a clinically plausible time sequence between onset of the AE

and administration of the investigational product, but the AE could also be attributed to concurrent or underlying disease, or the use of other drugs or procedures. Possibly related should be used when the investigational product is one of several biologically plausible AE

causes.

Definitely Related:

The AE is clearly related to use of the investigational product.

